9.3 POPULATIONS FOR ANALYSES

Data from all subjects who receive at least one dose of study medication will be included in all efficacy and safety analyses.

9.4 STATISTICAL ANALYSES

9.4.1 GENERAL APPROACH

Descriptive statistics (mean and standard deviation, median, minimum, and maximum) for all outcome measures at each timepoint will be calculated.

Plots of the data, (including spaghetti plots) will be used to visualize patterns in the data. Additional post hoc exploratory analyses may be carried out.

9.4.2 ANALYSIS OF THE PRIMARY EFFICACY ENDPOINT

The 11-item Alzheimer's Disease Assessment Scale-cognitive subscale (ADAS-cog/11) has been a standard cognitive outcome measure in clinical trials for patients with mild to moderate AD. Total scores range from 0–70, with higher scores indicating greater cognitive impairment. The average expected worsening (increase) on this scale over 6 months in this population is in the range of 2 to 3 points. A clinically meaningful improvement (decrease) on this scale has been deemed to be 4 or more points. Based on previous results in patients with mild to moderate AD maintained on stable treatment with a cholinesterase inhibitor, the expected responder rate at 25 weeks (defined as improvement in ADAS-cog/11 score of ≥ 4 points) is 20% (0.20) (Rockwood et al. 2007).

A patient will be considered a responder if they improve by a minimum of 4 points on the ADAS-cog/11 scale at 25 weeks compared to baseline. The proportion of patients who respond to daratumumab will be estimated, and the associated 95% exact binomial confidence interval will be calculated.

9.4.3 ANALYSIS OF THE SECONDARY ENDPOINTS

Secondary Efficacy Endpoints will consist of the proportion of subjects who are unchanged or improved from baseline to 25 weeks on ADAS-cog/12 score (standard 11 items plus delayed word recall), Mini Mental State Examination (MMSE) score, Clinical Dementia Rating Scale Sum of Boxes (CDR-SB) score, and AD Composite Score (ADCOMS).

All analyses will be carried out separately for each secondary endpoint listed above.

For each measure of cognitive response, a patient will be classified as stable or improved if the score at 25 weeks is the same or better than at baseline. The proportion of patients who are stable/improved, and the associated 95% exact binomial confidence interval will be calculated.

9.4.4 SAFETY ANALYSES

The proportion of patients with one or more treatment-emergent adverse events will be estimated, and the associated 95% exact binomial confidence interval will be calculated.

The proportion of patients with one or more treatment-emergent serious adverse events will be estimated, and the associated 95% exact binomial confidence interval will be calculated.

9.4.5 BASELINE DESCRIPTIVE STATISTICS

Descriptive statistics (mean and standard deviation, median, minimum, and maximum for continuous factors; frequency and proportion for categorical factors) for demographic and clinical factors (including age, sex, years of education, and baseline MMSE score) will be calculated.

9.4.6 PLANNED INTERIM ANALYSES

Not applicable.

9.4.7 SUB-GROUP ANALYSES

Not applicable.

9.4.8 TABULATION OF INDIVIDUAL PARTICIPANT DATA

Not applicable.

9.4.9 TERTIARY/EXPLORATORY ANALYSES

The pattern of cognitive response to daratumumab, as measured by ADAS-cog/11, ADAS-cog/12, MMSE, CDR-SB, and ADCOMS, will be examined over time at baseline (prior to the start of daratumumab treatment), 12 weeks (midpoint), 25 weeks (endpoint), and 36 weeks (12 weeks after completion of treatment).

For each measure of cognitive response, repeated measures analysis of variance (RMANOVA) where time (baseline, 12 weeks, 25 weeks, 36 weeks) is the within subjects effect, and there is not between subjects effect, will be used to examine the changes in each outcome over time.

CD38 expression in circulating CD8+ T-cells will be measured with flow cytometry at baseline and at 25 weeks. The paired t-test will be used to examine whether there is a change at 25 weeks vs baseline.

Cerebral metabolite ratios will be measured on single-voxel protein magnetic resonance spectroscopy from the precuneus and posterior cingulate region at baseline and at 25 weeks, including:

- N-acetylaspartate/creatinine (NAA/Cr)
- myo-inositol/creatinine (ml/Cr)
- choline/creatinine (Cho/ml)
- N-acetylaspartate/myo-inositol (NAA/ml)

All analyses will be carried out separately for each metabolite ratio endpoint listed above. The paired t-test will be used to examine whether there is a change at 25 weeks vs baseline for each factor listed above.

If the usual assumptions of the proposed parametric models are not met, an appropriate transformation or a suitable non-parametric method will be used.

10 SUPPORTING DOCUMENTATION AND OPERATIONAL CONSIDERATIONS

10.1 REGULATORY, ETHICAL, AND STUDY OVERSIGHT CONSIDERATIONS

10.1.1 INFORMED CONSENT PROCESS

10.1.1.1 CONSENT/ASSENT AND OTHER INFORMATIONAL DOCUMENTS PROVIDED TO PARTICIPANTS

Consent forms describing in detail the study intervention, study procedures, and risks are given to the subject, their study partner, and the subject's legally authorized representative (if applicable), and written documentation of informed consent is required prior to starting any study-related procedure.

The following consent materials are submitted with this protocol:

- Subject Informed Consent Form
- Study Partner Information and Consent Form

10.1.1.2 CONSENT PROCEDURES AND DOCUMENTATION

Informed consent is a process that is initiated prior to the individual's agreeing to participate in the study and continues throughout the individual's study participation. Potential participants will be provided with a copy of the informed consent document ahead of research participation. This will allow the subject and their legally authorized representative (if applicable) the necessary time to carefully review detailed information about the study procedures, risks, and benefits, and ask questions or express concerns prior to making a decision about whether to participate. Prior to the initiation of any screening or study-specific procedures, the investigator or his representative will explain the nature of the study to the subject, their study partner, and the subject's legally authorized representative (if applicable), and answer all questions regarding this study. Participants will be informed that participation is voluntary and that they may withdraw from the study at any time, without prejudice. The rights and welfare of the participants will be protected by emphasizing to them that the quality of their medical care will not be adversely affected if they decline to participate in this study. Due to the inherent nature of the study population, with cognitive impairment due to Alzheimer's disease, it is anticipated that many of these subjects will lack decisional capacity to provide informed consent. Accordingly, all potential subjects will be assessed for capacity to provide informed consent by one of the study physicians, who are either neurologists or geriatric psychiatrists with extensive experience in

assessing decisional capacity. If a subject is determined to lack capacity to provide informed consent, surrogate consent will need to be obtained from a legally authorized representative. In that instance, the subject will also need to provide written assent to participate in the study. Each informed consent will be reviewed, signed and dated by the subject or their legally authorized representative (if applicable), the person who administered the informed consent, and any other signatories according to local requirements. A separate informed consent will also be reviewed, signed, and dated by the subject's study partner prior to beginning any study related screening activities. A copy of each informed consent will be given to the subject and their study partner and each original will be placed in the subject's study chart. An entry must also be made in the subject's dated source documents to confirm that informed consent was obtained prior to any study-related procedures and that the subject and study partner received signed copies.

10.1.2 STUDY DISCONTINUATION AND CLOSURE

This study may be temporarily suspended or prematurely terminated if there is sufficient reasonable cause. Written notification, documenting the reason for study suspension or termination, will be provided by the suspending or terminating party to study participants, investigator, funding agency, the Investigational New Drug (IND) sponsor, and regulatory authorities. If the study is prematurely terminated or suspended, the Principal Investigator (PI) will promptly inform study participants, the Institutional Review Board (IRB), and Janssen Scientific Affairs, LLC, and will provide the reason(s) for the termination or suspension. Study participants will be contacted, as applicable, and be informed of changes to study visit schedule.

Circumstances that may warrant termination or suspension include, but are not limited to:

- Determination of unexpected, significant, or unacceptable risk to participants
- Demonstration of efficacy that would warrant stopping
- Insufficient compliance with protocol requirements
- Data that are not sufficiently complete and/or evaluable
- Determination that the primary endpoint has been met
- Determination of futility

The study may resume once concerns about safety, protocol compliance, and data quality are addressed, and satisfy Janssen Scientific Affairs, LLC, the IRB, and/or the Food and Drug Administration (FDA).

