9.2 SAMPLE SIZE DETERMINATION

This is a pilot study, the purpose of which is explore whether there is a clinically meaningful efficacy signal for daratumumab in patients with mild to moderate Alzheimer's disease. The proposed sample size of 15 patients is based on feasibility and availability of resources, and not on a formal power calculation.

The following table provides estimates of proportions and their associated 95% confidence intervals for a sample size of 15 subjects.

N=15			
Observed Number Responding	Observed Proportion Responding	Exact Lower 95% Confidence Interval	Exact Upper 95% Confidence Interval
0	0.000	0.000	0.218
1	0.067	0.002	0.319
2	0.133	0.017	0.405
3	0.200	0.043	0.481
4	0.267	0.078	0.551
5	0.333	0.118	0.616
6	0.400	0.163	0.677
7	0.467	0.213	0.734
8	0.533	0.266	0.787
9	0.600	0.323	0.837
10	0.667	0.384	0.882
11	0.733	0.449	0.922
12	0.800	0.519	0.957
13	0.867	0.595	0.983
14	0.933	0.681	0.998
15	1.000	0.782	1.000

For a sample size of 15 subjects, if 7 patients respond, the lower limit of the exact 95% binomial confidence interval is 0.213, (i.e., we are 95% certain that the true proportion with a response is no lower than 0.213). Based on previous results in patients with mild to moderate AD maintained on stable treatment with a cholinesterase inhibitor, the expected responder rate at 25 weeks (defined as improvement in ADAS-cog/11 score of ≥ 4 points) is 20% (0.20) (Rockwood et al. 2007). Therefore, if 7 or more of 15 subjects respond, we would consider further study of daratumumab warranted.

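### Do the efficacy and futility grounds for termination in Section 10.1.2 undermine a plan with no interim analysis?

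*Combined protocol and SAP*

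**What the plan says.** Section 10.1.2 introduces its list with "Circumstances that may warrant termination or suspension include, but are not limited to". Three of the six entries concern efficacy: "Demonstration of efficacy that would warrant stopping", "Determination that the primary endpoint has been met" and "Determination of futility". On follow-up after closure it says only: "Study participants will be contacted, as applicable, and be informed of changes to study visit schedule". Section 9.4.6 marks planned interim analyses as not applicable.

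The one decision rule is in Section 9.2: "Therefore, if 7 or more of 15 subjects respond, we would consider further study of daratumumab warranted". Its basis is that "if 7 patients respond, the lower limit of the exact 95% binomial confidence interval is 0.213", which is above the expected rate of 0.20. Sections 9.1 and 9.4.2 treat the primary endpoint as a proportion to be estimated with an exact 95% interval. Section 9.3 puts everyone who has received a dose into all efficacy and safety analyses. Section 7.1 keeps subjects who stop injections in the scheduled assessments. Section 6.3 confirms that the trial is open-label, and Section 5.5 expects 15 subjects over 18 months.

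**The concern.** A proportion that is only to be estimated cannot be *met* without a threshold, and none is attached to that word. The same holds for efficacy and futility: no count, bound or timing is given. The independent monitor's remit in Section 10.1.6 is safety. Because the trial is open-label, staff can watch responders accumulate, and about two thirds of the week-25 outcomes could be known before enrolment ends.

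Two things would be at stake. First, the estimated responder rate, which is the study's aim, could be biased by stopping on a favourable or unfavourable run. Second, the go decision is written for 15 subjects. A stop with fewer might leave it unclear whether the rule is 7 responders or any result whose lower limit exceeds 0.20. Taken alone, 5 of 8 (lower limit 0.245) and 6 of 12 (0.211) would pass the second reading with fewer than 7 responders.

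**Working it through.** **Inputs.** From Section 9.2: N = 15, go at 7 or more, reference rate 0.20, exact 95% intervals. From Section 5.5: 15 subjects in 18 months. From Section 1.3: the week-25 visit on Day 176. Assumptions, since the plan gives none: even accrual, a look after each outcome, and the stopping rules tried below.

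**The plan's own figure.** The exact lower limit for x of n is the 0.025 quantile of Beta(x, n − x + 1). For 7 of 15 it is 0.2127, agreeing with the stated 0.213. For 6 of 15 it is 0.163, so 7 is the smallest count whose limit clears 0.20. All 16 rows of the Section 9.2 table reproduce.

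**Fixed-size false-go.** P(X ≥ 7 | n = 15, p = 0.20) = Σ C(15, k) 0.2^k 0.8^(15−k) over k = 7 to 15 = 0.0181.

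**Subjects in the pipeline.** 18/15 = 1.2 months per subject. Day 176 is 5.78 months, and 5.78/1.2 = 4.8, so about 5 subjects are enrolled but unread at any look. By month 18, (18 − 5.78)/1.2 ≈ 10 outcomes are known.

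**Stopping on the counts Section 9.2 implies.** Seven responders settle the go rule whatever follows. Nine non-responders settle it the other way, since 15 − 9 = 6 < 7. Neither stop can alter the decision, so false-go stays at 0.0181. The mean estimated rate, by exact enumeration of response sequences with the 5 pipeline subjects counted and n capped at 15, is:

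| Stop at | True rate | Mean estimate |
|---|---|---|
| 7 responders | 0.40 | 0.4007 |
| 7 responders | 0.50 | 0.5019 |
| 7 responders | 0.60 | 0.6040 |
| 9 non-responders | 0.20 | 0.1988 |
| 9 non-responders | 0.30 | 0.2995 |
| 9 non-responders | 0.40 | 0.3998 |

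The largest shift is 0.6040 − 0.60 = 0.4 points. With both counts in force the range is −0.1 to +0.4 points over true rates of 0.20 to 0.60. Minimum interval coverage for the 7-responder stop is 95.1%. With 4 pipeline subjects instead of 5, the largest shifts are 0.8 points (7 responders) and 0.4 points (9 non-responders).

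**The 5 of 8 and 6 of 12 examples.** Adding the pipeline, a stop at 5 of 8 ends at n = 8 + 5 = 13, and a stop at 6 of 12 ends at the cap of 15. The smallest count with a lower limit above 0.20 is 7 at each of n = 13, 14 and 15, so the two readings of the go rule coincide. With 4 in the pipeline, the first example ends at n = 12, where 6 would suffice, so the agreement depends on the accrual assumption.

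**A harsher, assumed rule: stop once the lower limit exceeds 0.20, with 5 counted.** With looks from the first subject, false-go is 0.0172 and the mean at a true 0.50 is 0.520. The rest depends on how early looking starts (true rate 0.50):

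| Looks start at subject | Upward shift | Chance that the limit exceeds 0.20 with fewer than 7 responders |
|---|---|---|
| 1 | 2.0 points | 15% |
| 5 | 1.5 points | 10% |
| 8 | 0.6 points | 0 |

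Starting at subject 1 allows a stop at 3 responders out of 3. With 4 in the pipeline, the 15% becomes 21%.

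**The case for a change.** The strongest case for acting is that the terms really are undefined and that Section 9.3 does not settle what happens at closure. It says whose data are analysed, not that dosed subjects will be brought back at week 25 once the study has been terminated. Section 7.1 covers stopping injections, not stopping the study. If pipeline outcomes were lost, the effects would grow. Stopping at 7 responders would give a mean of 0.6296 at a true 0.60, a shift of 3.0 points. The lower-limit rule with a look after every subject would give false-go of 4.4%, a mean of 0.59 at a true 0.50 and minimum coverage of 93.6%. Stopping on an observed proportion of at least 7/15, with looks from subject 5, could take false-go to 11.7%. Removing the three entries and ruling out such stops would take only a few words.

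The missing definitions stand as a fact, and so does the silence on follow-up after closure. The materiality does not. Those larger figures need a rule that appears nowhere in the documents, and also need dosed subjects left out, against the plain sense of Section 9.3. Nor is the remedy free. A commitment never to stop on observed efficacy or futility would keep subjects enrolled and dosed after 9 non-responders had made 7 of 15 impossible. That is a real burden in a population where Section 5.5 expects many to lack decisional capacity.

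**Conclusion.** No change is needed. Section 10.1.2 reserves discretion and schedules nothing; Section 9.4.6 says no interim analysis is planned; both can be true, and no stated figure is wrong. What is missing is detail that an analyst can fill sensibly: the only threshold is the Section 9.2 count, and all dosed subjects belong in the analysis.

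On that reading false-go stays at 1.8%, and the rate moves by at most about 0.4 points (0.8 with 4 pipeline subjects). Either is negligible beside an interval of 0.213 to 0.734 at 7 of 15 in a feasibility-sized pilot. Ruling out every such stop would exchange this small risk for continued exposure after the decision was settled, a trade-off the sponsor may fairly leave as it is.

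The conclusion rests on even accrual over 18 months, on dosed subjects being followed to week 25 and counted, and on true rates between 0.20 and 0.60. It would weaken if the study were in fact stopped on a handful of early responders and the remaining outcomes went uncollected, but nothing in the plan points to that.

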10.1.3 CONFIDENTIALITY AND PRIVACY

Participant confidentiality and privacy is strictly held in trust by the investigator, research staff, and the sponsor. This confidentiality is extended to cover testing of biological samples in addition to the clinical information relating to participants. Therefore, the study protocol, documentation, data, and all other information generated will be held in strict confidence. No information concerning the study or the data will be released to any unauthorized third party without prior written approval of subject or their legally authorized representative.

All research activities will be conducted in as private a setting as possible.

The study monitor, other authorized representatives of the Institution, representatives of the Institutional Review Board (IRB), regulatory agencies, or the pharmaceutical company supplying study product may inspect all documents and records required to be maintained by the investigator, including but not limited to, medical records (office, clinic, or hospital) and pharmacy records for the participants in this study. The clinical study site will permit access to such records.

The study participant's contact information will be securely stored at the clinical site for internal use during the study. At the end of the study, all records will continue to be kept in a secure location for as long a period as dictated by the reviewing IRB, Institutional policies, or regulatory requirements.

The study data entry and study management systems used by clinical site research staff will be secured and password protected. The Feinstein Institute for Medical Research will be used as a central location for data processing and management. Vanderbilt University, with collaboration from a consortium of institutional partners, has developed a software toolset and workflow methodology for electronic collection and management of research and clinical trial data. REDCap (Research Electronic Data Capture) data collection projects rely on a thorough study-specific data dictionary defined in an iterative self-documenting process by all members of the research team with planning assistance from the Biostatistics Unit of the Feinstein Institute for Medical Research. The interactive development and testing process results in a well-planned data collection strategy for individual studies. REDCap servers are housed in a local data center at the Feinstein and all web-based information transmission is encrypted. REDCap was developed specifically around HIPAA-Security guidelines and is recommended to Northwell Health's researchers by our Clinical Research Service, Research Compliance Office and Institutional Review Board. REDCap has been disseminated for use locally at other institutions and currently supports more than 2500 active institutional partners and other institutions in more than 100 countries (www.projectredcap.org). De-identified research data may be stored on portable electronic devices (e.g. laptops, tablets, flash drives, etc.). All such devices will be encrypted as per Northwell Health policy (www.projectredcap.org).

Certificate of Confidentiality:

To further protect the privacy of study participants, a Certificate of Confidentiality (CoC) will be issued by the National Institutes of Health (NIH). This certificate protects identifiable research information from forced disclosure. It allows the investigator and others who have access to research records to refuse to disclose identifying information on research participation in any civil, criminal, administrative, legislative, or other proceeding, whether at the federal, state, or local level. By protecting researchers and institutions from being compelled to disclose information that would identify research participants, Certificates of Confidentiality help achieve the research objectives and promote participation in studies by helping assure confidentiality and privacy to participants.

10.1.4 FUTURE USE OF STORED SPECIMENS AND DATA

Data collected for this study will be analyzed and stored at the Feinstein Institute for Medical Research.

When the study is completed, access to study data will be provided through the Feinstein Institute for Medical Research.

10.1.6 SAFETY OVERSIGHT

Safety oversight will be under the direction of an Independent Safety Monitor (ISM), a physician with relevant expertise whose primary responsibility is to provide independent safety monitoring in a timely fashion. This is accomplished by review of adverse events, immediately after they occur or are reported, with follow-up through resolution. The ISM will be notified of SAEs by the study team within 24 hours of knowledge of the event. The ISM will be notified of unexpected problems as soon as possible, but within 5 business days of knowledge of the event. The ISM will be notified within 15 business days of severe (NCI CTCAE Grade 3 or 4) nonserious AEs. The study team will report aggregate mild to moderate (NCI CTCAE Grade 1 or 2) nonserious AEs to the ISM at 4-month intervals. The ISM evaluates individual and cumulative participant data when making recommendations regarding the safe continuation of the study. The ISM will be independent from the study conduct and free of conflict of interest, or measures should be in place to minimize perceived conflict of interest.

